6.6 Sampling technique and recruitment

All eligible IBD patients visiting the Gastroenterology Department of any of the study centres that will participate in patient recruitment (Mediclinic City Hospital, Mediclinic Parkview Hospital and Rashid hospital) under the care of any of the coinvestigator consultant gastroenterologists during the period of recruitment (12 months from the start date of the study – to be decided following ethical approval) will be offered to take part in the study.

RJ

Version 3.2. Effective Date: 04 December 2021

Patients will be randomised (1:1) to receive Frondanol (one 1000 mg capsule twice daily) or placebo (in a similar capsule) as an adjunct to their standard therapy using a randomization number sequence generator. This will be conducted by the study statistician using the Microsoft Excel random number generator and will only be shared with the study coordinator.

All patients and investigators, excluding the study coordinator, will be blinded to treatment allocation.

6.7 Intervention

Patients will be randomized (1:1) to receive Frondanol (one 1000 mg capsule twice daily) or placebo (in a similar capsule) as an adjunct to their standard therapy by a designated study coordinator. Both Frondanol and placebo capsules will be supplied by Coastside Bio Resources, Stonington, ME, USA. The placebo capsules will be red/brown-coloured gelatin capsules (similar in texture and colour to the Frondanol capsules), but will contain an inert (inactive) substance called food-grade corn starch, which will not interact with the immune system. Patients will be instructed to take one capsule of their assigned medication twice daily.

6.8 Consent

Informed consent will be obtained following consultation with one of the coinvestigator consultant gastroenterologists to assess eligibility for the study. The study will be explained to the patient by the consultant gastroenterologist and informed consent will be obtained prior to treatment. Patients will be requested to inform the study coordinator or the consultant gastroenterologist of any adverse events following the start of treatment. A direct phone number will be given to patients so that they are able to call the study coordinator in case of any adverse events. The study coordinator, PI and co-investigator gastroenterologists will have thorough understanding of the protocol and patient population. Retention of patients will be encouraged through discussion at the time of consent and throughout the duration of the study regarding the importance of adherence with the study procedures. The study will be conducted in accordance with the IRB-approved protocol and with the guidelines of the Good Clinical Practices (GCP). Patients may withdraw from the study at any time, and no further data will be collected from him/her or analyzed for the purpose of this research.

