6.2 Study setting

Patients will be seen in-person at the Gastroenterology Department of any of the study centres that will participate in patient recruitment (Mediclinic City Hospital, Mediclinic Parkview Hospital and Rashid hospital) by one of the coninvestigator consultant gastroenterologists at screening and randomization (T0), at a follow-up visit at 3 months (T1), and at a second follow-up visit at 6 months (T2). Routine blood tests as well as an extra sample for research

RJ

Version 3.2. Effective Date: 04 December 2021

purposes will be obtained at these timepoints. Colonoscopies will be performed as part of the routine clinical practice and these include acquisition of routine biopsies, typically 10-15 from each patient. A few additional biopsies (2-4) will be needed for our studies, to be snap frozen and analyzed in MBRU research laboratory facilities. IRB approval for these additional biopsies and serological testing is being sought from both Mediclinic City Hospital's REC, MBRU-IRB and DHA-REC. It is hoped that the routine colonoscopies can be scheduled prior to starting the study treatment and 6 months later.

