6.13 Subject Identification

All patient data and specimen will be de-identified and coded with the unique study number of the patient. The code linking the study number with the patient will be accessed by the study coordinator only and maintained at MBRU in a database and will not be provided to the PI or her research team. Patient data will be collected using protocol-specific case report forms (CRFs), which will be used to create electronic CRFs (e-CRFs). Clinical records for all patients, including CRFs, will be retained by the PI in a secure storage facility for ten years after the completion of the study. Paper data will be stored in a locked

RJ

Version 3.2. Effective Date: 04 December 2021

cabinet and electronic data will be stored on a password-protected computer in the custody of the PI. The data linking patient identifying information and their de-identified data will be in the custody of the study coordinator who will be unblinded. All patients will complete the following study visits: Screening (medical history, physical examination, vital signs and standard of care tests including blood and stool tests), baseline endoscopy (day 1 of treatment, date to be agreed between the gastroenterologist and patient), 3 months (routine monitoring with standard of care tests including blood and stool tests), 6 months (second endoscopy and standard of care tests including blood and stool tests).

 -
RJ

Version 3.2. Effective Date: 04 December 2021

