6.14 Study schedule

Table 1: Variables to be collected from participants

Method of data collection	Variables
Questionnaires	Mayo Score, IBDQ
Medical record	Symptoms
Blood samples	Routine blood tests as well as an extra sample (10 mL) for research purposes will be obtained at T0 (start of study), T1 (3 months) and T2 (6 months).
Stool samples	Routine stool sample will be collected for measurement of fetal calprotectin levels at the recruiting hospital at T0, T1 and T2.
Tissue samples	Colonoscopies will be performed as part of the routine clinical practice and these include acquisition of routine biopsies, typically 10-15 from each patient. A few additional biopsies (2-4) will be collected for our studies during routine colonoscopies when these are performed, then they will be snap frozen and analyzed in MBRU research laboratory facilities.

Table 2: Schedule of Activities

Variable	Visit # 1 (T0)	Visit # 2 (T1 – 3months)	Visit # 3 (T2 – 6 months)
Questionnaires	Mayo Score, IBDQ	Mayo Score, IBDQ	Mayo Score, IBDQ
Medical record	Symptoms	Symptoms	Symptoms
Blood samples	Routine blood tests as well as an extra sample (10 mL) will be obtained, stored and analyzed in MBRU research laboratory facilities.	Routine blood tests as well as an extra sample (10 mL) will be obtained, stored and analyzed in MBRU research laboratory facilities.	Routine blood tests as well as an extra sample (10 mL) will be obtained, stored and analyzed in MBRU research laboratory facilities.
Stool sample	Routine stool sample will be collected for measurement of fetal calprotectin levels at MCH	Routine stool sample will be collected for measurement of fetal calprotectin levels at MCH	Routine stool sample will be collected for measurement of fetal calprotectin levels at MCH
Tissue samples	If colonoscopy is performed for routine clinical practice at the start of the study, a few additional biopsies (2-4) will be collected for our studies, snap frozen and analyzed in	No tissue samples collected	If colonoscopy is performed for routine clinical practice at the end of the study, a few additional biopsies (2-4) will be collected for our studies, snap frozen and analyzed in

RJ

Version 3.2. Effective Date: 04 December 2021

	MBRU research laboratory facilities.	MBRU research laboratory facilities.
--	--------------------------------------	--------------------------------------

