10.2 Benefits to participants

Currently, treatment of IBD relies on minimizing symptoms and improving quality of life through the control of disease progression and complications. Treatments for IBD include aminosalicylates, high-dose oral steroids, azathioprine, cyclosporine or methotrexate. Alternatively for severe refractory disease, anti-TNF drugs such as infliximab, adalimumab and golimumab can be used. More recently, integrin antagonists such as vedolizumab and etrolizumab have shown some promising results. However, these drugs have significant systemic side effects that reduce their tolerability. Moreover, up to 40% of patients still exhibit non-response to therapy, and these treatment-refractory patients would require alternative therapeutic approaches. Frondanol is a widely available neutraceutical extract from the edible sea cucumber which has been shown to have potent anti-inflammatory (as well as anti-cancer) effects in rats, in particular in the colon and in humans. Therefore,

RJ

Version 3.2. Effective Date: 04 December 2021

we decided to investigate the anti-inflammatory effects of Frondanol in human IBD patients. Over the past 25 years, it is estimated that more than 3 million Frondanol capsules have been consumed on the human market with no reported side effects. An even larger amount has been consumed on the veterinary market without a single reported incident. LD50 for Frondanol has not be ascertained because no deaths were observed following the administration of large amounts to rats, to the point that no more could be given due to gastric distention (unpublished observations by our group). All patients in the proposed study will continue to receive standard therapy. If proven beneficial, Frondanol, will be a useful supplement in treating the underlying chronic gut inflammation in IBD patients, increasing the likelihood of patients remaining in remission and potentially providing an effective, natural and safe treatment for treatment naive patients in the future.

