10.3 Costs and Payments

Participants will not receive study incentives (compensation) nor will they incur costs for participating in this study.

10.4 Safety Monitoring:

In the unlikely event that side effects occur, patients will be requested to immediately inform the study coordinator/research nurse, PI or consultant gastroenterologist. A direct phone number will be given to patients so that they are able to call the study coordinator or assigned nurse in case of any adverse events. Depending on the severity of the event, the participant will be instructed whether to report to the Gastroenterology unit at the study site or to head to the emergency department of one of the hospitals covered by the trial's liability insurance, for further investigation and possible treatment.

Simultaneously, the PI, assisted by the clinical gastroenterologists on the team, and taking into account any other medical information available, will perform a causality assessment to ascertain whether the adverse event was related to participation in the trial. If the adverse event is deemed to be related to participation in the trial, the participant will be advised to immediately stop taking the study medication (whether Frondanol or placebo) and will be provided with the necessary medical care until the issue is resolved.

In the unlikely event that the adverse event is deemed to be caused by Frondanol and if the assessment by the study team results in a doubt that further adverse events may occur with other participants, the trial will be immediately suspended, and all participants will be informed and required to stop taking their assigned study medication and await further instructions from the PI or trial coordinator.

Any serious or unexpected adverse event will be reported by the PI to all ethical committees that have approved this study, no later than 24 hours for

RJ

Version 3.2. Effective Date: 04 December 2021

life threatening events and no later than 10 working days for non-life-threatening events. Reports to the involved ethical committees will include advice from PI as to whether in her opinion (supported by the opinions of the study team's gastroenterologists):

- The adverse event was related to the protocol or the study drug
- The adverse event necessitates an amendment to the study protocol and/or patient information/consent form

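### Adverse-event reporting is left to the patient, with no adverse-event item at T1 or T2 and no summary by arm, so counts by arm may be incomplete

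*Combined protocol and SAP*

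**What the plan says.** Section 6.8 gives the reporting method: "Patients will be requested to inform the study coordinator or the consultant gastroenterologist of any adverse events following the start of treatment". It adds: "A direct phone number will be given to patients so that they are able to call the study coordinator". Sections 7, 10.4 and 10.6 use similar wording: "patients will be requested to immediately inform the study coordinator/research nurse, PI or consultant gastroenterologist". They also name an assigned nurse as a second person on the phone line. In each of these places the patient starts the report; none of them tells staff to ask.

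Patients are seen in person at 3 months (T1) and 6 months (T2) under 6.2. The visit list in 6.13 and Tables 1 and 2 in 6.14 say what is collected: questionnaires ("Mayo Score, IBDQ"), symptoms from the medical record, routine and research bloods, stool, and tissue where a routine colonoscopy is done. There is no adverse-event item.

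Section 8.2 describes the efficacy analyses and names no adverse-event summary. The objectives in section 5 contain no safety outcome. Section 10.4 covers what follows a known event: causality assessment, stopping of study medication, possible suspension of the trial, and reporting to the ethics committees. Sections 3 and 10.2 look ahead, if benefit is shown, to "potentially providing an effective, natural and safe treatment for treatment naive patients in the future".

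**The concern.** Events that patients volunteer are usually a subset of those they would mention if asked, and the size of the shortfall cannot be known from the trial's own data. Three consequences follow.

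- Adverse-event counts by arm may be too low by an unknown factor. If the shortfall is equal in both arms, a true difference shrinks. If it is unequal, a difference can appear or vanish.
- The shortfall could be unequal. The coordinator who answers the phone holds the open randomisation sheet (6.3) and is described as unblinded (6.13), so the first person to hear of an event may know the allocation.
- The causality and suspension steps in 10.4 act only on events that become known, so the trial's own safeguards depend on the reporting step.

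A randomised placebo arm offers a controlled check on an expectation of no side effects that now rests on market history (section 7). Weak ascertainment would waste part of that opportunity.

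**Working it through.** **The documents side by side.** There is no planned figure to reproduce: 8.1 gives no event rate, effect size or power. The question is whether any scheduled procedure amounts to asking about adverse events.

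| Item at T1 and T2 | Where | Role the protocol gives it |
|---|---|---|
| Symptoms | Tables 1 and 2 | Compared between arms (objective 2a) |
| Routine bloods | 6.2, Tables 1 and 2 | CBC, ESR, CRP and albumin compared between arms (objective 2b) |
| Mayo score, IBDQ | Tables 1 and 2 | Questionnaires |
| Adverse-event question | Not listed | None |

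The first two could reveal some adverse events, but nothing designates them as adverse-event ascertainment or says that results are reviewed for that purpose.

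**Illustration of size.** The one input from the documents is n = 50 on Frondanol (6.4). The true risk p and the capture rate c (the share of affected patients whose event is recorded) are assumptions; the documents give neither. The recorded risk is p × c, taking patients as independent.

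*Zero events recorded.* The one-sided 95% upper bound on the recorded risk is 1 − 0.05^(1/50) = 0.0582. Dividing by c gives the bound on the true risk:

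- c = 100%: 5.8%
- c = 60%: 0.0582 / 0.6 = 9.7%
- c = 40%: 0.0582 / 0.4 = 14.5%

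*Chance of recording at least one case* = 1 − (1 − p × c)^50:

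| True risk p | c = 100% | c = 60% | c = 40% |
|---|---|---|---|
| 5% | 1 − 0.95^50 = 92% | 1 − 0.97^50 = 78% | 1 − 0.98^50 = 64% |
| 3% | 1 − 0.97^50 = 78% | 1 − 0.982^50 = 60% | 1 − 0.988^50 = 45% |

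*Limit set by size alone.* With full capture, the chance of seeing at least one case is 1 − 0.98^50 = 64% for a 2% event and 1 − 0.99^50 = 39% to 40% for a 1% event. Better ascertainment does not change this.

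**The case against.** The best defence is that the protocol offers more than a phone line and claims less than a safety result. Several stronger readings are tempting and should be set aside.

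- *Events are captured only by phone.* A reader might infer this, but patients may also tell the gastroenterologist, the PI or the research nurse, and T1 and T2 are in-person visits.
- *The trial makes a safety claim that it cannot support.* It has no safety objective or endpoint. The wording in sections 3 and 10.2 is conditional on proven benefit and describes a possible future, and the expectation of no side effects rests on market use.
- *Patients are told that side effects are unlikely, which discourages reporting.* That word is the protocol's own, in 7, 10.4 and 10.6. The consent-form extracts quoted in the protocol do not contain it, and the full form was not available.
- *Laboratory changes go uncaptured.* Routine bloods are taken at every visit, and several of them are compared between arms. The table entry for symptoms is also not restricted to IBD symptoms.

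The protocol also commits to GCP (6.8, 9.4, 10.1) and site monitoring (9.4), and the case report forms mentioned in 6.13 may hold an adverse-event page that cannot be seen here. Finally, the capture rates are assumed, so the arithmetic does not itself prove a defect.

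All of this stands, and it narrows the point. It does not supply a scheduled enquiry, a stated use of the symptoms and bloods for this purpose, or a by-arm summary.

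**Conclusion.** The point holds in a limited form. As written, adverse-event reporting is entirely patient-initiated. One route leads to an unblinded person, no adverse-event item is scheduled at T1 or T2, and 8.2 plans no summary by arm. Counts by arm may therefore be incomplete, and possibly unequally so. A low count could not later be used to support the safe-treatment prospect.

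The documents do not fix the size of the loss. At assumed capture of 60% or 40%, the bound after zero recorded events moves from 5.8% to 9.7% or 14.5%. The practical difficulty is that c would be unknown, so nobody could say which bound applies. Part of the limitation is the sample size and would remain after any change to ascertainment. This is a gap that should be closed; it does not affect the efficacy objectives.

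**What to change.** **Table 2 (6.14).** Add an adverse-event row at T1 and T2: one standard, open, non-leading question put to every patient by blinded staff, plus review of the routine blood results already taken for adverse changes. Add a CRF page to record the answers.

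**Section 8.2.** Add a descriptive table of patients with any, serious and treatment-related adverse events, by randomised arm, among all who took study capsules.

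**Sections 6.8 and 6.10.** These end collection and analysis of further data at withdrawal, which could remove the patients in whom an event prompted the withdrawal. Reconcile them with the new table by stating that events recorded up to withdrawal, including any that led to it, are counted.

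**Cost.** A few minutes at visits already planned, one CRF page and one table, with no new visits or samples. The downside is more minor events to record.

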6.9 Voluntary participation

The following paragraph is included in the consent form regarding voluntary participation:

“Your participation in the study is entirely voluntary and you may refuse to participate or discontinue participation at any time without penalty or loss of

RJ

Version 3.2. Effective Date: 04 December 2021

benefits to which you would normally be entitled. Your decision about whether or not to participate in the study will not affect your relationship with MBRU or medical treatment at the hospital/clinic, if applicable.”

6.10 Criteria for subject withdrawal

Patients may withdraw from the study at any time, and no further data will be collected from him/her or analyzed for the purpose of this research.

6.11 Withdrawal from the study

The following paragraph is included in the consent form regarding withdrawal from the study:

“You are at liberty to withdraw from the research study at any stage, without prejudice. Should any new information become available that may affect your willingness in participation, you will be informed in a timely manner. However, the principal investigator or designee may take you out of the study at any time with or without your agreement. This may happen for example if it is in your best medical interest to stop your participation, or if the study is canceled. If you wish to withdraw from the study, any collected data will be safely stored for a minimum of three years following the completion of the study then discarded in a confidential manner that does not risk identifying your personal information.”

6.12 Premature discontinuation of the study

The whole study may be discontinued prematurely in the event of the following:

- Mediclinic decision that continuation of the study is unjustifiable for medical or ethical reasons
- Poor enrolment of subjects making completion of the study within an acceptable time frame unlikely

DHCR and the MBRU-IRB and MCME-REC will be informed about the discontinuation of the study in accordance with applicable regulations. The whole study may be terminated or suspended upon the request of DHCR.

6.13 Subject Identification

All patient data and specimen will be de-identified and coded with the unique study number of the patient. The code linking the study number with the patient will be accessed by the study coordinator only and maintained at MBRU in a database and will not be provided to the PI or her research team. Patient data will be collected using protocol-specific case report forms (CRFs), which will be used to create electronic CRFs (e-CRFs). Clinical records for all patients, including CRFs, will be retained by the PI in a secure storage facility for ten years after the completion of the study. Paper data will be stored in a locked

RJ

Version 3.2. Effective Date: 04 December 2021

cabinet and electronic data will be stored on a password-protected computer in the custody of the PI. The data linking patient identifying information and their de-identified data will be in the custody of the study coordinator who will be unblinded. All patients will complete the following study visits: Screening (medical history, physical examination, vital signs and standard of care tests including blood and stool tests), baseline endoscopy (day 1 of treatment, date to be agreed between the gastroenterologist and patient), 3 months (routine monitoring with standard of care tests including blood and stool tests), 6 months (second endoscopy and standard of care tests including blood and stool tests).

 -
RJ

Version 3.2. Effective Date: 04 December 2021

6.14 Study schedule

Table 1: Variables to be collected from participants

Method of data collection	Variables
Questionnaires	Mayo Score, IBDQ
Medical record	Symptoms
Blood samples	Routine blood tests as well as an extra sample (10 mL) for research purposes will be obtained at T0 (start of study), T1 (3 months) and T2 (6 months).
Stool samples	Routine stool sample will be collected for measurement of fetal calprotectin levels at the recruiting hospital at T0, T1 and T2.
Tissue samples	Colonoscopies will be performed as part of the routine clinical practice and these include acquisition of routine biopsies, typically 10-15 from each patient. A few additional biopsies (2-4) will be collected for our studies during routine colonoscopies when these are performed, then they will be snap frozen and analyzed in MBRU research laboratory facilities.

Table 2: Schedule of Activities

Variable	Visit # 1 (T0)	Visit # 2 (T1 – 3months)	Visit # 3 (T2 – 6 months)
Questionnaires	Mayo Score, IBDQ	Mayo Score, IBDQ	Mayo Score, IBDQ
Medical record	Symptoms	Symptoms	Symptoms
Blood samples	Routine blood tests as well as an extra sample (10 mL) will be obtained, stored and analyzed in MBRU research laboratory facilities.	Routine blood tests as well as an extra sample (10 mL) will be obtained, stored and analyzed in MBRU research laboratory facilities.	Routine blood tests as well as an extra sample (10 mL) will be obtained, stored and analyzed in MBRU research laboratory facilities.
Stool sample	Routine stool sample will be collected for measurement of fetal calprotectin levels at MCH	Routine stool sample will be collected for measurement of fetal calprotectin levels at MCH	Routine stool sample will be collected for measurement of fetal calprotectin levels at MCH
Tissue samples	If colonoscopy is performed for routine clinical practice at the start of the study, a few additional biopsies (2-4) will be collected for our studies, snap frozen and analyzed in	No tissue samples collected	If colonoscopy is performed for routine clinical practice at the end of the study, a few additional biopsies (2-4) will be collected for our studies, snap frozen and analyzed in

RJ

Version 3.2. Effective Date: 04 December 2021

	MBRU research laboratory facilities.	MBRU research laboratory facilities.
--	--------------------------------------	--------------------------------------

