7. SAFETY CONSIDERATIONS

The recommended dose on the marketed neutraceutical product of Frondanol is 1000 mg twice daily. Over the past 25 years more than 3 million 1000 mg capsules have been consumed in the human market, with no reported side effects. Hence, we based the dosing for our study on the marketed recommended dose, as we do not anticipate any side effects. We will be excluding patients with allergy to seafood or marine products to avoid the risk of allergic reactions.

Colonoscopies performed in this study are considered part of routine care and not for research purposes. The overall expected rate of serious complications (bleeding or perforation) from routine colonoscopies is 2-3 per 1000 procedures (Lee and Salzman, 2020). The only additional procedure that is done for the research is to take several additional biopsies after all routine biopsies are taken. The expected increase in risk from taking these several additional biopsies is considered to be very small and likely insignificant. The consent form will state that the “increased risk of taking additional biopsies, for the purposes of this research, after all routine biopsies are taken is considered to be very small.”

In the unlikely event that side effects occur, patients will be requested to immediately inform the study coordinator/research nurse, PI or consultant gastroenterologist. A direct phone number will be given to patients so that they are able to call the study coordinator or assigned nurse in case of any adverse events. Depending on the severity of the event, the participant will be instructed whether to report to the Gastroenterology unit at the study site or to head to the emergency department of one of the hospitals covered by the trial's liability insurance, for further investigation and possible treatment.

Additional risks to the study subjects would be embarrassment or discomfort in answering items on questionnaires to be completed. Participants will be instructed not to answer any questions that they feel uncomfortable with.

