8.2 Statistical methods

All statistical analyses will be carried out using SPSS Software (Armonk, New York, USA). Potential confounders such as age and sex will be controlled for during the analysis phase. A per-protocol analysis including only participants who have a full data set will be used to assess the efficacy of Frondanol treatment in lowering inflammatory markers. An intention-to-treat analysis will also be conducted including patients who drop out before the study ends, for whom we will use last observation carried forward (LOCF) i.e. we will impute the last observed data for all subsequent (missing) observation points. For quantitative data, within-group and between-group comparisons will be analyzed using the General linear Repeated Model (MANOVA), which would allow for adjustment of potential confounders such as age and sex. Data will be plotted as mean \pm SEM and p values <0.05 will be considered statistically significant.

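### Sections 6.13 and 6.14 disagree on who has colonoscopies, and 8.2 handles the resulting gaps badly: its per-protocol set is tied to no outcome, and LOCF gives dropouts zero tissue change

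*Combined protocol and SAP*

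**What the plan says.** All references are to the combined protocol and SAP.

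- **6.13** introduces its visit list with "All patients will complete the following study visits". The list includes a baseline endoscopy and "6 months (second endoscopy and standard of care tests including blood and stool tests".
- **6.14** makes study tissue conditional. Table 1 says the extra biopsies "will be collected for our studies during routine colonoscopies when these are performed". Table 2 repeats the condition at T0 and at T2 ("If colonoscopy is performed for routine clinical practice at the end of the study"). At T1 the entry is "No tissue samples collected". Blood and stool are scheduled at T0, T1 and T2 without any such condition.
- **6.2** treats colonoscopy as routine practice and leaves its timing open: "It is hoped that the routine colonoscopies can be scheduled prior to starting the study treatment and 6 months later".
- **Section 7** adds: "Colonoscopies performed in this study are considered part of routine care and not for research purposes". This fits the conditional reading but does not state it.
- **8.2** says: "A per-protocol analysis including only participants who have a full data set will be used". This is the analysis meant to assess efficacy on inflammatory markers. An intention-to-treat analysis is to be run as well. It includes patients who drop out and fills all their later missing points by LOCF.
- **6.8 and 6.10** say that once a patient withdraws, no further data are collected or analysed.
- **Section 5** compares biopsy mRNA and protein (Objective 1) and endoscopic and histologic features (Objective 2d) between arms at baseline and six months.

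**The concern.** Sites cannot tell from the text whether a 6-month colonoscopy is due for every patient. If the conditional wording governs, some patients will have no paired tissue, and those who do are a subset selected partly after randomisation. The plan does not acknowledge this.

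The two rules in 8.2 then matter. A per-protocol set that can require tissue may discard good blood and stool data in the analysis that carries the efficacy assessment. LOCF enters a constructed no-change value for dropouts in the tissue part of the first-listed objective and in Objective 2d.

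**Working it through.** **Inputs.** 50 patients per arm (Sections 1 and 6.4) and a significance level of 0.05 (8.2; two-sided assumed, since the plan does not say). Section 8.1 is headed as a power calculation but gives no effect size, SD, power or dropout rate, so there is no planned figure to reproduce. All shares of patients below are assumptions.

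**1. Schedule.** If every patient has both endoscopies (6.13), the condition in Table 2 is always met and has no function. If the condition has a function, 6.13 is not true of all patients. The texts cannot both stand as written.

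**2. Per-protocol blood and stool analyses, if a full data set means all outcomes.** The difference detectable with 80% power in a two-sample t-test is approximately (1.96 + 0.84) × √(2/n) SD. For n = 50 this is 2.80 × 0.20 = 0.56; the exact t-based value is 0.566.

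| Share with paired tissue (assumed) | n per arm | Detectable difference, SD (t-based) |
|---|---|---|
| 100% | 50 | 0.566 |
| 80% | 40 | 0.634 |
| 60% | 30 | 0.736 |
| 40% | 20 | 0.909 |

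Intention-to-treat blood and stool analyses are unaffected.

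**3. LOCF on tissue, equal dropout.** Let q be the dropout share in each arm and s the share of completers with T2 tissue. Assume that T0 tissue is equally available in dropouts and completers, that dropouts would have had the completers' effect, and that completers without T2 tissue are left out (8.2 offers LOCF to dropouts only). Dropouts contribute zero change, so the difference shrinks by q / (q + (1 − q)s).

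| s | q = 10% | q = 20% | q = 30% |
|---|---|---|---|
| 100% | 10% | 20% | 30% |
| 60% | 16% | 29% | 42% |
| 40% | 22% | 38% | 52% |

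Example with 50 per arm, all with T0 tissue, q = 20% and s = 60%: 10 copied values and 40 × 0.6 = 24 real changes, so 10/34 = 29%.

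**4. LOCF on tissue, unequal dropout.** Take s = 100%.

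- No treatment effect, a common change of −0.5 SD, dropout 10% and 30%: the arm means become −0.5 × 0.9 = −0.45 and −0.5 × 0.7 = −0.35. This is a spurious difference of 0.10 SD.
- True changes of −1.0 SD (10% dropout) and −0.5 SD (30% dropout): LOCF gives −0.90 and −0.35. The difference is 0.55 SD instead of the true 0.50, so a real effect is inflated.

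**5. Blood and stool.** A patient who leaves before month 3 has only a T0 value here too, and LOCF again imputes zero change. A patient who leaves after month 3 has a T1 value to carry.

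**6. Gaps in the rules.** 8.2 has no rule for completers without T2 tissue. LOCF has nothing to carry for a dropout without T0 tissue. Sections 6.8 and 6.10 may bar the analysis of withdrawn patients that 8.2 plans; the wording leaves open whether data collected before withdrawal may be used.

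**The case against.** **The full data set may be harmless.** It could mean every item that fell due for that patient, or it could be applied outcome by outcome. A patient without a colonoscopy would then stay in the set. This stands: the loss in step 2 arises under one reading only. A reader might infer that the trial would lose its blood and stool data; the documents do not support that, because the intention-to-treat analysis keeps these patients.

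**LOCF on blood and stool.** Because these have a T1 sample, a reader might infer that the zero-change problem is confined to tissue. The schedule does not support this, since patients who leave before month 3 have no T1 sample. The problem is universal for dropouts' tissue but not exclusive to tissue.

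**Direction.** A reader might infer that LOCF always dilutes the effect. Step 4 shows otherwise, and nothing in the documents supports equal dropout.

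**Size.** Crediting dropouts with the completers' effect is doubtful. If they stop the capsules, their own six-month effect may be smaller, and so would the shrinkage. The larger figures in step 3 also combine unfavourable assumed shares. Step 2 uses an unadjusted t-test rather than the planned covariate-adjusted repeated-measures model, and 0.57 SD is not a target of the plan. These points stand.

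**Remedy.** Confining tissue outcomes to patients with paired colonoscopies gives up the only intention-to-treat tissue analysis in favour of a selected subset. This also stands, and is why a sensitivity analysis and a caveat are needed.

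**Conclusion.** The concern holds, with limits. Three things are firm: the conflict between 6.13 and 6.2/6.14; a per-protocol set tied to no outcome; and exactly zero imputed tissue change for any dropout with T0 tissue, provided 6.8 and 6.10 allow that patient's data to be analysed.

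The size is not firm. Under the step 3 assumptions, shrinkage equals the dropout share when all completers have T2 tissue and is larger when fewer do. With unequal dropout the bias may go either way. The per-protocol loss for blood and stool depends on how 8.2 is read. The size and direction of selection bias in the paired subset cannot be estimated from the documents.

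This should be corrected before analysis. Pilot status does not remove the need, because biopsy outcomes are part of the first-listed objective.

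**What to change.** 1. Reconcile 6.13 with 6.2 and 6.14 on who has a colonoscopy at T0 and T2, and reconcile 6.8 and 6.10 with the use of dropouts' data in 8.2.
2. In 8.2, define the analysis set separately for each outcome, so that blood, stool and symptom analyses never require a biopsy.
3. Do not use LOCF for tissue, endoscopic or histologic outcomes. For blood and stool, do not carry a T0-only value forward; use all observed visits instead.
4. Analyse tissue outcomes in all randomised patients with paired colonoscopies, adjusted for the baseline value. Report by arm the paired numbers and the reason for each T2 colonoscopy.
5. Add a simple sensitivity analysis for missing T2 tissue, covering completers as well as dropouts.
6. If colonoscopy stays conditional, state that selection into the paired subset may bias the result in an unknown direction. Step 4 documents this selection but does not remove it.

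The cost is protocol and analysis wording, one CRF item for the reason for the T2 colonoscopy, and one extra analysis. No procedure is added. The downside is that tissue results rest on fewer patients and support more modest claims.
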